## nAb

- nAb ever-positive versus nAb never-positive
- nAb: treatment-induced nAb versus nAb never-positive or baseline nAb positive

Data listings will include immunogenicity data together with relevant PK, safety and efficacy data.

### PK parameters and immunogenicity status

The following analyses will include patients in both the immunogenicity analysis set and in the PK parameter analysis set. The PK endpoints pertinent to the immunogenicity analyses are  $C_{\text{trough}}$  and  $C_{\text{max}}$ .

Blood samples for avelumab PK will be collected as outlined in the “Schedule for Pharmacokinetic Sample Collection” table of the Schedule of Assessments section of the protocol.

$C_{\text{trough}}$  and  $C_{\text{max}}$  will be summarized descriptively (n, mean, SD, CV, median, minimum, maximum, geometric mean, its associated CV, and 95% CI) by nominal time and ADA status. Linear-linear and log-linear plots of mean and median for  $C_{\text{trough}}$  and  $C_{\text{max}}$  over nominal time and by ADA status will be presented.

Among patients with treatment-induced ADA, analyses will be conducted to assess whether  $C_{\text{trough}}$  and  $C_{\text{max}}$  have any changes before and after the first positive ADA assessment. To be included in this analysis, patients must have the same PK parameter available both before and after the first positive ADA assessment. Relative PK day will be calculated as:

$$(\text{PK assessment nominal day}) - (\text{first positive ADA assessment nominal day}).$$

Nominal day is the protocol scheduled timing for an assessment. For example, if  $C_{\text{trough}}$  is collected on Day 1 of Cycle 2 and the first positive ADA result is observed on Day 1 of Cycle 3, then the relative PK day for this  $C_{\text{trough}}$  is -14. Linear-linear and log-linear plots of mean and median for  $C_{\text{trough}}$  and  $C_{\text{max}}$  over relative PK day will be presented.

As data permit, the analyses described above will be repeated for nAb.

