Other Clinical Assessments										
Follow-up for Axitinib Dosing Compliance ¹⁸					X ¹⁸ (D5 ±3 days)	X ¹⁸ (D5 ±3 days)			X ¹⁸ (D5 ±3 days)	
Adverse Events ¹⁹				X						
Concomitant Medications/Treatments ²⁰	X	(X)	X	X	X	X	X	X	X	
Enrollment by Study Treatment²¹										
Avelumab ²²				X ²¹		X ²¹			X ²¹	
Axitinib ²²				X						
Other Samplings										
Pharmacokinetics ²³			X	X	X	X		X (Cycles 3, 4, 6, 8, then Q12W, until cycle 50)		
CCI										
Mandatory Archival FFPE Tumor Tissue ²⁵	X									

Visit Identifiers ¹	Screening	Lead-In PK Period (Single-Agent Axitinib) ²		Study Treatment (1 cycle = 14 days)					
				Cycle 1		Cycle 2		Cycles ≥3 (until amend. #4 approval)	Cycles ≥3 (after amend. #4 approval)
	≤28 Days Prior to Enrollment	Day 1	Day 7	Day 1	Day 8 (±1 day)	Day 1 (±3 days)	Day 8 (±1 day)	Day 1 (±3 days)	Day 1 (±3 days)
Mandatory Recent or De Novo FFPE Tumor Tissue Block ²⁶	X								
Anti-Avelumab Antibodies and Neutralizing Antibodies ²⁷				X		X		X (Cycles, 3, 4, 6, 8, then Q12W, until cycle 50)	

ACTH = adrenocorticotrophic hormone; ECG = electrocardiogram; ECOG = Eastern Cooperative Oncology Group; FFPE = formalin-fixed and paraffin-embedded; HBV = hepatitis B virus; HCV = hepatitis C virus; PK = pharmacokinetics; Q6W = every 6 weeks; Q12W = every 12 weeks.

Footnotes for Schedule of Activities for SCREENING and STUDY TREATMENT Periods Patients participating in Dose Finding Phase and up to 8 additional patients enrolled for further pharmacokinetic (PK) assessment
1. Visit Identifiers: All assessments should be performed prior to the start of study treatment unless otherwise indicated. Acceptable time windows for performing each assessment are described in the column headers.
2. Lead-In PK Period: All patients in the Dose Finding Phase and up to approximately 8 additional patients enrolled for further PK assessment.
3. Informed Consent: Must be obtained prior to undergoing any study-specific procedure.
4. Medical/Oncological History: To include information on prior systemic adjuvant or neoadjuvant therapy regimens, surgery, and radiation therapy.
5. Baseline Signs/Symptoms: To be recorded predose on Lead-in Day 1. Patients will be asked about any signs and symptoms experienced within the 14 days prior to study enrollment.
6. Physical Examination: Includes an examination of major body systems and weight (height included at Screening only).

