19. **De Novo FFPE Tumor Tissue Block:** A *de novo* (ie., fresh biopsy) tumor sample should be collected at the time of discontinuation of either drugs and at the End of Treatment/Withdrawal, unless clinically contraindicated. Tumor tissue from cytologic sampling (eg, fine needle aspiration, including FFPE cell pellet material), is not adequate and should not be submitted. The *de novo* biopsy(ies) should be formalin-fixed and paraffin-embedded as per routine (see Study Manual), and the resulting FFPE tissue block(s) or slides if blocks cannot be provided (see [Section 6.1.1](#) for details) should be submitted to the Central Laboratory. See [Section 6.1.1](#) and [Section 7.4.1](#).
20. **Anti-Avelumab Antibodies (Anti-Drug Antibodies, ADAs) and Neutralizing Antibodies (Nab):** One blood sample (3.5 mL) for anti-avelumab antibodies (and simultaneous PK draws for measurement of avelumab) will be collected at the Day 30 Follow-up visit after the end of avelumab treatment. All the samples that are positive for ADA may also undergo characterization for Nab. Also see the [Schedule for Pharmacokinetic Sample Collection](#) Table. See [Section 7.3](#).

SCHEDULE FOR PHARMACOKINETIC SAMPLE COLLECTION

Pharmacokinetic samples are to be obtained on the same day as all other scheduled assessments outlined in the [Schedule of Activities](#) table.

Protocol Activity	Axitinib								Avelumab in Combination with Axitinib												
									Cycle 1		Cycles 2 and 3		Cycle 4						Cycle 6	Cycle 8 and Every 12 weeks Thereater until cycle 50	Day 30 Follow-Up
	Lead-in Day 7								Day 1	Day 8 (±1 day)	Day 1 (±3 days)		Day 1 (±3 days)						Day 1 (±3 days)	Day 1 (±3 days)	
Hours post dose	0 ^f	1	2	3	4	6	8	0 ^f	1	168	0 ^f	0 ^f	1	2	3	4	6	8	0 ^f	0 ^f	
PK for axitinib ^a	x	x	x	x	x	x	x					x	x	x	x	x	x				
PK for avelumab ^b								x	x ^d	x ^c	X	x	x ^d					x	x	x	
ADAs ^c								x			X	x						x	x	x	

PK=pharmacokinetics; ADAs=anti-drug antibodies
 Note that PK samples for avelumab and anti-avelumab-antibodies (ADA) will be collected from all patients in the study. Axitinib PK samples will be collected from all patients in the Dose Finding Phase and up to approximately 8 additional patients enrolled to assess the effect of avelumab on the PK of axitinib.

- One sample (3 mL) collected at each time point for axitinib.

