### **6.2.6. Immunogenicity Endpoints**

All analyses described below are performed for all treatment groups combined.

Blood samples for avelumab immunogenicity testing will be collected pre-dose on Cycle 1, 2, 3, 4, 6 and 8. Subsequently, testing should be performed approximately every 12 weeks. All samples should be drawn within 2 hours before start of avelumab infusion. Additional samples for anti-avelumab antibodies (and simultaneous PK draws for measurement of avelumab) will be collected at the Day 30 Follow-up visit after the end of avelumab treatment.

Samples positive for ADA will be analyzed for titer and may be analyzed for nAb. As of the finalization of this SAP, the nAb assay is not yet available, therefore the analyses of nAb data described in the following sections will only be conducted contingent upon assay and data availability at the time of reporting.

Patients will be characterized into different ADA categories based on the criteria defined in [Table 7](#).

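### The before/after-ADA avelumab PK analysis admits patients as their own controls but names only cross-patient mean and median plots, so the onset groups behind the before and after points differ partly or wholly

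*SAP*

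**What the plan says.** The passage is in SAP 6.2.6.3, under PK parameters and immunogenicity status. For patients with treatment-induced ADA it asks whether avelumab Ctrough and Cmax "have any changes before and after the first positive ADA assessment". Entry is paired: "To be included in this analysis, patients must have the same PK parameter available both before and after the first positive ADA assessment".

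Samples are then placed on a relative day, which is the PK nominal day minus the nominal day of the first positive ADA. On the nominal day the SAP says "Nominal day is the protocol scheduled timing for an assessment". The named outputs are plots of mean and median Ctrough and Cmax "over relative PK day will be presented". The section specifies no within-patient ratio or difference, no individual profiles, no n per relative day and no grouping of relative days.

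SAP 6.2.6 gives the ADA schedule: "Blood samples for avelumab immunogenicity testing will be collected pre-dose on Cycle 1, 2, 3, 4, 6 and 8", and after that "Subsequently, testing should be performed approximately every 12 weeks". Pre-dose avelumab PK follows the same cycles; the last column group of the Protocol's Schedule for Pharmacokinetic Sample Collection is headed "Cycle 8 and Every 12 weeks Thereater until cycle 50". That table marks end-of-infusion samples, the source of Cmax, only at Cycle 1 Day 1 and Cycle 4 Day 1.

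**The concern.** The question concerns change within a patient, and the entry rule treats it that way. The plots then average across whoever has a sample on each relative day. Because the visits are 14, 28 or 84 days apart, the onset visit decides which relative days a patient can supply. A step in the plotted mean can then reflect who is in the average and not what happened to anyone's exposure.

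Immunogenicity of avelumab is a stated secondary objective, and this is the only analysis of avelumab exposure that uses ADA-positive patients as their own controls. The summary by nominal time and ADA status in the same section compares different patients, so it does not fill the gap. The risk is that a change in the plot is taken for an ADA effect on exposure, or that a real within-patient fall is masked.

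**Working it through.** **Inputs.** Cycles last 14 days (Protocol, Schedule of Activities). Pre-dose PK and ADA are taken at Cycles 1, 2, 3, 4, 6, 8, 14, 20 and so on to 50. End-of-infusion PK is taken at Cycles 1 and 4. SAP Table 2 defines Ctrough as the pre-dose concentration during multiple dosing, so the first usable trough is taken as Cycle 2 Day 1. The Day 30 follow-up sample is set aside.

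**Reproducing the SAP's example.** Nominal day of Cycle c Day 1 = 1 + 14(c - 1). This gives days 1, 15, 29, 43, 71, 99, 183 and so on. A Cycle 2 trough with first positive ADA at Cycle 3 has relative day 15 - 29 = -14, as the SAP states.

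**Ctrough: who supplies each day.** Subtracting each onset day from each trough day, for onset at Cycles 3 to 8:

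| Relative days | Before | After | Shared onset groups |
|---|---|---|---|
| -14 / +14 | C3, C4 | C3 | C3 |
| -28 / +28 | C4, C6, C8 | C4, C6 | C4, C6 |
| -42 / +42 | C6 | C3 | none |
| -56 / +56 | C6, C8 | C4 | none |
| -70 / +70 | C8 | C3 | none |

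Onset at Cycle 14 or later adds nothing within 70 days except at day 0, where every onset group is present. Onset at Cycle 2 has no earlier on-treatment trough and drops out.

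**Cmax.** Sample days are 1 and 43.
- Onset C2: 1 - 15 = -14 and 43 - 15 = +28.
- Onset C3: 1 - 29 = -28 and 43 - 29 = +14.
- Onset C4: 1 - 43 = -42 and 43 - 43 = 0.

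Each point is one onset group. Each group that qualifies supplies both its own before and its own after point, but the groups interleave on the axis. Whether C4 qualifies depends on day 0, which the SAP does not classify. ADA is drawn pre-dose and Cmax after the infusion, so by the clock the Cycle 4 Cmax follows the ADA sample.

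**A case with no change in anyone.** Let four patients have constant troughs of 10, 20, 30 and 40 (arbitrary units), with onset at C3, C4, C6 and C8.
- Day -14: (10 + 20)/2 = 15; day +14: 10; apparent change -33%.
- Day -28: (20 + 30 + 40)/3 = 30; day +28: (20 + 30)/2 = 25; apparent change -17%.
- Day -56: (30 + 40)/2 = 35; day +56: 20; apparent change -43%.

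Every within-patient ratio is exactly 1.00.

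**Simulation, illustrative only.** The documents give no ADA count, CV, within-patient correlation or onset distribution. Assumed: log-normal troughs with total CV 50%, onset equally likely at C3, C4, C6 and C8, no ADA effect, and 5 or 10 ADA patients. The paired summary is the geometric mean of (first trough after / last before). An apparent change is a ratio below 0.70 or above 1.43.

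| n | Correlation | Plotted +28/-14 | Plotted +28/-28 | Paired |
|---|---|---|---|---|
| 5 | 0.5 | 36% | 26% | 9% |
| 10 | 0.5 | 21% | 13% | 2% |
| 5 | 0.8 | 31% | 16% | 1% |
| 10 | 0.8 | 17% | 6% | 0% |

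At correlation 0.5 the 5th to 95th percentile range of the plotted +28/-14 ratio is about 0.51 to 2.0 (n = 5) and 0.6 to 1.6 (n = 10). The paired ratio gives 0.71 to 1.41 and 0.78 to 1.28. The median plotted +28/-14 ratio is 1.00. Part of the extra spread arises because each plotted day uses only some of the patients.

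**The case against.** A reader might infer that the before and after points always come from different patients, or that the plots are biased. The documents support neither. The -14/+14 and -28/+28 trough pairs share onset groups, day 0 holds everyone, and each qualifying Cmax group can be matched to itself. With no link between exposure and onset time the median ratio stays at about 1.00, so the distortion is noise. It becomes bias only if exposure is related to onset time, and the documents say nothing on that.

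A second tempting reading is that patients first positive at Cycle 2 enter as zero troughs at day -14, because SAP 5.3.1.1 sets values below quantification to zero. That requires the sample before the first infusion to count as a Ctrough, which strains Table 2's definition. It needs clarifying and is not a demonstrated error.

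The simulation also depends on its assumptions. The SAP names no +28/-14 contrast, and -28/+28 is milder. If every onset fell at Cycle 3, the excess would nearly vanish (11% at -14/+14 against 9% paired, n = 5, correlation 0.5).

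There are mitigations. The listings in 6.2.6.3 put PK beside immunogenicity data, so a paired look is possible for a few patients. SAP 5.3.1.1 withholds summary statistics at time points with more than half the data missing, which might remove thin days if unsampled relative days count as missing; the SAP does not say. Neither supplies a paired summary. The objection limits the size of the point but leaves the mismatch between entry rule and output.

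**Conclusion.** The point stands in limited form. That the composition changes from one relative day to the next follows from the sampling schedule and needs no assumption. The size does: with 5 to 10 ADA patients, CV 50% and evenly spread onset, a false apparent change at +28/-14 is roughly 17% to 36%, against 0% to 9% for the paired ratio. Fewer onset visits or the -28/+28 contrast would narrow that gap.

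Dose mix plays no part, since SAP section 6 records that only DL1, with and without lead-in, was tested. No hypothesis test or decision depends on the result, and at most about 55 patients are expected. The priority is low to moderate.

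**What to change.** In SAP 6.2.6.3:

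1. For each eligible patient, compute the ratio of the first on-treatment Ctrough after the first positive ADA to the last one before it. For Cmax, use Cycle 4 / Cycle 1. Report the geometric mean ratio with a 95% CI and n. SAP 6.2.3.1 and 6.2.3.2 already use matched pairs and geometric mean ratios for axitinib.
2. Show connected individual profiles by relative PK day, with n per day. If the mean and median curves are kept, print n beneath them.
3. State whether day-0 samples count as before or after, separately for the pre-dose trough and the end-of-infusion Cmax. The Cmax rule decides whether Cycle 4 onsets enter.
4. State that the sample before the first avelumab infusion is not a Ctrough.

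The cost is SAP wording and minor programming, with no new data or visits. Patients first positive at Cycle 2 then have no before-trough and contribute only to Cmax. A paired ratio still includes any time trend unrelated to ADA, and the text should say so.

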### Safety and immunogenicity status

The following analyses will include patients in the immunogenicity analysis set.

The frequency (number and percentage) of patients with each of the following will be presented by ADA status.

- TEAEs, by SOC and PT
- TEAEs leading to dose reduction of avelumab, by SOC and PT

CCI [REDACTED]  
[REDACTED]  
[REDACTED]  
[REDACTED]  
[REDACTED]

- | [REDACTED]
- | [REDACTED]  
[REDACTED]
- | [REDACTED]  
[REDACTED]
- | [REDACTED]
- | [REDACTED]

CCI [REDACTED]  
[REDACTED]  
[REDACTED]  
[REDACTED]

[REDACTED]  
[REDACTED]  
[REDACTED]  
[REDACTED]  
[REDACTED]  
[REDACTED]

[REDACTED]

[REDACTED]  
[REDACTED]  
[REDACTED]

[REDACTED]

CCI [REDACTED]  
[REDACTED]  
[REDACTED]  
[REDACTED]  
[REDACTED]  
[REDACTED]  
[REDACTED]  
[REDACTED]  
[REDACTED]  
[REDACTED]

CCI

A horizontal black bar redacting a line of text.

CCI

A large black rectangular redaction covering the majority of the page's content.

CCI

A black rectangular redaction covering a section of text.

CCI

A black rectangular redaction covering a section of text.

CCI

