#### **5.2.7. Definition of on-treatment period**

Safety endpoints will be summarized based on the on-treatment period unless otherwise specified.

On-treatment period is defined as the time from the first dose of study treatment through minimum (30 days + last dose of study treatment, start day of new anti-cancer drug therapy – 1 day).

Safety data collected outside the on-treatment period as described above will be listed and flagged in listings but not summarized.

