**Table 7 Patients Characterized Based on Anti-Drug Antibody Results (ADA Status)**

Category	Definition	Subjects at Risk (Denominator for Incidence)
ADA never-positive	No positive ADA results at any time point; ADA-negative patients (titer < cutpoint)	Number of patients with at least one valid ADA result at any time point
ADA ever-positive	At least one positive ADA result at any time point; ADA-positive patients (titer ≥ cutpoint)	Number of patients with at least one valid ADA result at any time point
Baseline ADA positive	A positive ADA result at baseline	Number of patients with valid baseline ADA result
Treatment-boosted ADA	A positive ADA result at baseline and the titer ≥ 8×baseline titer at least once after treatment with avelumab	Number of patients with valid baseline ADA results and at least one valid post-baseline ADA result
Treatment-induced ADA	Patient is ADA-negative at baseline and has at least one positive post-baseline ADA result; or if patient does not have a baseline sample, the patient has at least one positive past-baseline ADA result	Number of patients with at least one valid post-baseline ADA result and without positive baseline ADA result (including missing, NR)
Transient ADA response	If patients with treatment-induced ADA have (a single positive ADA result or duration between first and last positive result <16 weeks) and ADA result at the last assessment is not positive.	Number of patients with at least one valid post-baseline ADA result and without positive baseline ADA result (including missing, NR)
Persistent ADA response	If patients with treatment-induced ADA have duration between first and last positive ADA result ≥16 weeks or a positive ADA result at the last assessment	Number of patients with at least one valid post-baseline ADA result and without positive baseline ADA result (including missing, NR)

ADA: anti-drug antibody, NR = not reportable.

Patients will be characterized into different nAb categories based on the criteria in [Table 8](#). For nAb, treatment-boosted is not applicable since no titer result is available.

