#### **6.2.6.3. Analysis of PK, safety and efficacy by immunogenicity status**

The following ADA and nAb status will be used for the analyses described below.

ADA

- ADA ever-positive versus ADA never-positive
- ADA: treatment-induced ADA versus ADA never-positive or baseline ADA positive

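### SAP 6.2.6.3: TEAE percentages by ever/never ADA status mix any ADA effect with time on treatment, so the positive group is expected, though not certain, to show more events even if ADA has no effect

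*SAP*

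**What the plan says.** SAP 6.2.6.3 sets two ADA contrasts: "ADA ever-positive versus ADA never-positive", and "ADA: treatment-induced ADA versus ADA never-positive or baseline ADA positive". SAP Table 7 defines ever-positive as "At least one positive ADA result at any time point". Under SAP 6.2.6 the samples are pre-dose at Cycles 1, 2, 3, 4, 6 and 8. "Subsequently, testing should be performed approximately every 12 weeks", with one more at the Day 30 visit after avelumab ends. The protocol's Schedule of Activities stops the 12-weekly samples at cycle 50.

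The safety part of 6.2.6.3 reads: "The frequency (number and percentage) of patients with each of the following will be presented by ADA status". The first item is "TEAEs, by SOC and PT" and the second is TEAEs leading to avelumab dose reduction. The text after that is blacked out.

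The TEAE window is in SAP 5.2.7: "On-treatment period is defined as the time from the first dose of study treatment through minimum (30 days + last dose of study treatment", or to the day before new anti-cancer drug therapy if that is earlier. The readable safety text contains no landmark, no exposure adjustment and no restriction to events after first positivity. The neighbouring PK part of 6.2.6.3 does compare Ctrough and Cmax before and after the first positive result.

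**The concern.** The grouping variable is not known at the start of treatment. A patient joins the positive group by staying on avelumab long enough to seroconvert and be sampled, and the same time on drug is time at risk of a TEAE. The two percentages are therefore not expected to be equal under no ADA effect unless time on treatment is similar in the two groups. In addition, a TEAE in week 2 of a patient who first tests positive in week 38 is counted under positive status, although it came first. The treatment-induced contrast has the same structure.

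Immunogenicity is a secondary objective, and in the readable text this table is the summary that links ADA to safety. A reader could take a difference produced by treatment duration as a sign that ADA raises TEAE risk.

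**Working it through.** **Plan's own figure.** The documents give no figure for this table. The nearest is in SAP 5.1.1: with 40 patients and a true incidence of 6%, the chance of at least one AE is at least 90%. It reproduces: 1 − 0.94^40 = 0.916.

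**Inputs from the documents.** ADA samples at weeks 0, 2, 4, 6, 10 and 14, then every 12 weeks, plus Day 30; TEAE window to last dose + 30 days; 78-week cut-off (SAP 2); about 55 patients (SAP 5.1.1).

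**Opportunity to test positive.** Samples including Day 30: 5 with 6 weeks of avelumab, 7 with 14, 8 with 26, 10 with 52 and 12 with 78.

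**Assumptions (not in the documents).** Treatment duration, seroconversion and TEAE onset are independent, so ADA has no effect. Hazards are constant, positivity persists, and both drugs stop together.

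**Hand illustration.** Take seroconversion hazard 0.005/week and TEAE hazard 0.02/week. With T weeks of treatment and 30/7 = 4.3 weeks after it, the chance of being classed positive is 1 − exp(−0.005(T + 4.3)) and the chance of a TEAE is 1 − exp(−0.02(T + 4.3)).

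| T | Positive | TEAE |
|---|---|---|
| 6 weeks | 5.0% | 18.6% |
| 52 weeks | 24.5% | 67.6% |

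Suppose half the patients have each duration.
- TEAE among positives: (0.050 × 0.186 + 0.245 × 0.676) / (0.050 + 0.245) = 59%.
- TEAE among negatives: (0.950 × 0.186 + 0.755 × 0.676) / (0.950 + 0.755) = 40%.

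Within each duration ADA and TEAE are unrelated; the gap comes only from duration.

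**Simulation.** This used 400,000 patients per scenario and exponential duration with median 26, 52 or 78 weeks. Seroconversion hazard was 0.002, 0.005 or 0.01/week (7–41% ever-positive), and TEAE hazard was 0.005, 0.02 or 0.1/week.
- In all 27 scenarios the ever-positive percentage was higher, by 4 to 18 points (ratio 1.05–1.56).
- Median 52 weeks, seroconversion 0.005/week, TEAE 0.02/week: 69% vs 56%, with mean treatment 62 vs 45 weeks.
- Of the events in ever-positive patients, 53–87% preceded the first positive sample.

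**When the excess shrinks or reverses (ratio ever/never).**

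| Changed assumption | Ratio |
|---|---|
| All seroconversion in weeks 0–6 | 0.99–1.01 |
| Baseline positivity only | 1.00 |
| TEAEs concentrated in the first 12 weeks | 1.03–1.11 |
| TEAE ends avelumab in 10% of cases | 1.22–1.25 |
| 30% | 1.14–1.15 |
| 50% | 1.03–1.09 |
| 100% | 0.77–0.89 |

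**Against sampling error.** With 21% of 55 positive (about 12, leaving 43), the standard error of 69% minus 56% is √(0.69 × 0.31/12 + 0.56 × 0.44/43) = 0.15. The 13-point artefact is smaller than one standard error.

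**Checking remedies with no ADA effect.** Patient-time rates pooled over all time, after versus before first positivity, give ratios of 0.98–1.02 if hazards are constant. They fail if TEAEs cluster early:

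| TEAE hazard, weeks 0–8 then later | Planned percentages, ratio | Pooled rates, ratio |
|---|---|---|
| 0.05 then 0.005/week | 1.10 | 0.40 |
| 0.1 then 0.005/week | 1.05 | 0.25 |

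(Median 52 weeks, seroconversion 0.005/week.) Comparing by status at onset within bands of time since first dose gave 0.98–1.00, and a week-14 landmark gave 0.97–1.02, in the scenarios run for them.

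**The case against.** The strongest reply is that this is a descriptive table. SAP 5.1.1 plans no formal hypothesis test, the SAP attributes no event to ADA, and the artefact is within noise at this sample size. All of that stands. A reader might infer that the plan would produce a false-positive safety finding; the documents do not support this, because there is no test to be falsely positive.

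A reader might also infer that the positive group must show more events. That does not follow either. The documents give no seroconversion timing, treatment duration or TEAE hazard, and the excess disappears or reverses under plausible alternatives.

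A third tempting reading is that the SAP contains no time-ordered safety analysis at all. Part of the section is redacted, so its absence cannot be asserted. A supplementary analysis there would not change the bias in the readable table.

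SAP 6.2.6.3 also plans listings that combine immunogenicity and safety data, so event order can be checked patient by patient. This helps a careful reader but leaves the summary percentages as they are. Finally, patients may continue axitinib alone, which extends the TEAE window past the last avelumab dose. When this was checked, the ratio stayed at about 1.23.

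**Conclusion.** The point holds as a matter of interpretation. By the SAP's own definitions, status is acquired over treatment, earlier events are counted under it, and the readable text does not correct for either. Under no ADA effect the expected false excess is roughly 4 to 18 points if hazards are constant and seroconversion is spread over treatment. It is near zero if seroconversion is at baseline or in the first weeks, and negative if the event nearly always ends avelumab. These sizes rest on assumed durations and hazards. As a ratio the excess is smallest for very common TEAEs (1.05–1.14 at 0.1/week) and larger for less frequent terms. The change is worth making because it is cheap, but it concerns a secondary descriptive display and does not touch the primary endpoint.

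**What to change.** In the safety part of SAP 6.2.6.3, add one time-ordered display:

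- **(a) Landmark.** Classify patients by ADA results through Cycle 8 Day 1 (week 14). Count only TEAEs with onset after that day, in patients still in the on-treatment period.
- **(b) Status at onset.** Classify each TEAE by ADA status when it began, with time before the first positive sample counted as ADA-negative. Compare rates within bands of time since first dose, or use a time-dependent covariate on that time scale.

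Do not substitute patient-month rates pooled over all time: if TEAEs cluster early, they would make ADA look protective. Keep the ever/never and treatment-induced percentages as a secondary display labelled as not adjusted for exposure or timing.

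The cost is SAP wording and modest programming, since the SAP already uses first-positive ADA dates, AE onset dates and dosing dates. There are small downsides. Seroconversion is known only to lie between two samples, so some TEAEs after true conversion are assigned to negative time. The landmark drops earlier events and does not count later converters as positive. Counts will be small under either option.
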